the potential for progenitor cells to be harvested from the diaphysis of the humerus (deep humerus) has yet to be quantified. Thus, this the aim of this study is to analyze the cellular characteristics of cBMA from two extraction sites (PSIS and deep humerus) from patients undergoing standard-of-care arthroscopic rotator cuff repair surgery. Additionally, we aim to determine if patient positioning during PSIS harvest has any effect on the cellular content of collected cBMA.

2 Study Design

This is a single site, comparative quantitative analysis study of the cellular characteristics of bone marrow aspirate from two extraction sites (PSIS and deep humerus) from patients undergoing standard-of-care arthroscopic rotator cuff repair surgery. 30 total patients will be recruited through the Andrews Institute physician practices. Potential participants will be prescreened for inclusion and exclusion criteria through standard of care medical evaluations. Once a potential participant has agreed to be involved in the study, they will go through the described informed consent process. Patients meeting the inclusion criteria will have the study explained to them by one of the members of the research team, and they will be given an opportunity to participate if they are interested. No specific advertising or recruitment material will be utilized.

After the described screening and informed consent process have been completed, all participants will undergo standard-of-care arthroscopic rotator cuff repair surgery. During all surgeries, bone marrow will be aspirated from the PSIS and from the deep humerus. The first 15 participants will have bone marrow aspirated from the PSIS while in the prone position on the operating table. The final 15 participants will have bone marrow aspirated from the PSIS while in the lateral decubitus position on the operating table. Both cohorts will undergo deep humeral harvest intraoperatively in the lateral decubitus position. One mL of cBMA from each harvest site from each surgery will be removed and sent to the AREF Regenerative Medicine Center (RMC) for analysis. The remaining cBMA will be used to augment the rotator cuff repair surgery.

3 Objectives

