3.1 Primary Objective

The primary objective of this study is to determine whether the PSIS or deep humeral harvest produces a greater cellular harvest in patients undergoing rotator cuff repair.

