3.2 Secondary Objective

The secondary objective is to determine if prone verses lateral decubitus participant positioning influences the quantity of harvested cells from the PSIS.

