Descriptive statistics will be compiled for all numeral measures (Demographics, CBC, TNC, viability, CFU-F). Data will be analyzed for differences between experimental groups (PSIS v. deep humeral harvest, Prone vs. lateral decubitus positions) using 1-Way ANOVA and appropriate post-hoc analysis procedures (ex: Tukey's Honestly Significant Difference (HSD)). A significant p-value of < 0.05 for rejecting the null hypothesis will be used for all measures.

11 Quality Control and Assurance

All protocols will be monitored and analyzed data will be checked for accuracy by the principal investigator and /or a designated AREF research team member. All medical data will be kept in compliance with HIPAA guidelines.

12 References

1. Akpancar, S., et al., *The Current Perspectives of Stem Cell Therapy in Orthopedic Surgery*. Arch Trauma Res, 2016. **5**(4): p. e37976.
2. Marycz, K., et al., *Endurance Exercise Mobilizes Developmentally Early Stem Cells into Peripheral Blood and Increases Their Number in Bone Marrow: Implications for Tissue Regeneration*. Stem Cells Int, 2016. **2016**: p. 5756901.
3. Rochefort, G.Y., et al., *Multipotential mesenchymal stem cells are mobilized into peripheral blood by hypoxia*. Stem Cells, 2006. **24**(10): p. 2202-8.
4. Hauser, R.A. and A. Orloffsky, *Regenerative injection therapy with whole bone marrow aspirate for degenerative joint disease: a case series*. Clin Med Insights Arthritis Musculoskelet Disord, 2013. **6**: p. 65-72.
5. Hernigou, P., et al., *Biologic augmentation of rotator cuff repair with mesenchymal stem cells during arthroscopy improves healing and prevents further tears: a case-controlled study*. Int Orthop, 2014. **38**(9): p. 1811-8.
6. Hernigou, P., et al., *Cell therapy of hip osteonecrosis with autologous bone marrow grafting*. Indian Journal of Orthopaedics, 2008. **43**(1): p. 40-45.
7. Hernigou, P., et al., *Percutaneous autologous bone-marrow grafting for nonunions*. Journal of Bone and Joint Surgery, 2005. **87**(7): p. 1430-1437.
8. Saw, K.Y., et al., *Articular cartilage regeneration with autologous peripheral blood stem cells versus hyaluronic acid: a randomized controlled trial*. Arthroscopy, 2013. **29**(4): p. 684-94.
9. Vangsness, C.T., Jr., H. Sternberg, and L. Harris, *Umbilical Cord Tissue Offers the Greatest Number of Harvestable Mesenchymal Stem Cells for Research and Clinical Application: A Literature Review of Different Harvest Sites*. Arthroscopy, 2015. **31**(9): p. 1836-43.

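### Section 10's one-way ANOVA ignores the within-patient pairing, leaves the non-randomised position comparison without its humeral reference, and does not say whether the site effect is averaged over PSIS position

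*Protocol*

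**What the plan says.** Protocol section 2 plans that "30 total patients will be recruited through the Andrews Institute physician practices" and makes the design paired: "During all surgeries, bone marrow will be aspirated from the PSIS and from the deep humerus". PSIS position is set by order of entry: "The first 15 participants will have bone marrow aspirated from the PSIS while in the prone position on the operating table", then "The final 15 participants will have bone marrow aspirated from the PSIS while in the lateral decubitus position on the operating table". The humerus does not vary: "Both cohorts will undergo deep humeral harvest intraoperatively in the lateral decubitus position". Section 6 repeats this layout.

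Section 3.1 asks the study to "determine whether the PSIS or deep humeral harvest produces a greater cellular harvest in patients undergoing rotator cuff repair" and names no PSIS position. Section 3.2 asks whether "prone verses lateral decubitus participant positioning influences the quantity of harvested cells from the PSIS". The alternative hypothesis in section 4.2 expects a position effect.

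Section 10 lists the comparisons as "PSIS v. deep humeral harvest, Prone vs. lateral decubitus positions", to be tested by one-way ANOVA with a post-hoc procedure (Tukey's HSD as an example) at 0.05 for every measure. It names no patient term, no site-by-position term and no role for the humeral value in the position comparison.

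**The concern.** The stated method does not fit the stated design in three respects.

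- **Pairing.** The two sites are sampled in the same patient, but a one-way ANOVA treats the 60 samples as independent.
- **Position.** The prone and lateral groups are consecutive cohorts, not randomised ones. The protocol's own background says that yield depends on body mass and aspiration technique, and both could differ between early and late patients. The humeral sample is taken in the same position in all 30 patients, so it is the only in-trial reference for such shifts. The stated analysis cannot use it.
- **Meaning of the site effect.** In the first 15 patients site and position change together, and only the final 15 give a position-matched site contrast. If the PSIS samples are one group, the answer averages over two harvest positions, and the protocol does not say that this is what it wants.

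At stake are the sensitivity of the primary test, the credibility of the secondary result, and a clear reading of the primary estimate.

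**Working it through.** **Inputs from the protocol.** 30 patients, 15 + 15 = 30, both sites in each, humerus always lateral, alpha 0.05, one-way ANOVA. The protocol gives no power figure to reproduce.

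**Assumptions, none from the protocol.** Between-site correlation ρ of 0.3 to 0.7, equal SDs σ at the two sites, normal data (on the log scale where ratios are used), and illustrative effect sizes. Rejection rates come from simulation with at least 20,000 trials per setting.

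**1. Pairing.** The true variance of the mean PSIS-minus-humerus difference is 2σ²(1−ρ)/30. One-way ANOVA uses 2σ²/30, so its standard error is too large by 1/√(1−ρ): 1.20, 1.41 and 1.83 at ρ = 0.3, 0.5 and 0.7. With no effects at all, the nominal 5% site test rejects 2.2%, 0.6% and 0.1% of the time. A paired test stays at 5%.

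**2. Site contrast when the PSIS cohorts form one group.** Let s be the site contrast in lateral position and d the prone effect on PSIS.

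Pooled contrast = [15(s + d) + 15s]/30 = s + d/2

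For d = 0.5 SD the shift is 0.25 SD; for d = 1 SD it is 0.5 SD. On a ratio scale, a prone/lateral ratio of 1.3 multiplies the PSIS/humerus ratio by √1.3 = 1.14.

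**3. Position contrast under a shift between cohorts.** Let g be a change in case mix or practice that affects both sites equally.

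- PSIS only: d + g.
- Difference of within-patient differences: (d + g) − g = d.
- PSIS adjusted for the humeral value: with equal SDs the slope is ρ, so d + g − ρg = d + (1−ρ)g.

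Take d = 0 and a 1.4-fold shift with log SD 0.7: ln 1.4 / 0.7 = 0.336/0.7 = 0.48 SD. The PSIS-only test rejects about 25% of the time. The covariate-adjusted test rejects about 15%, 11% and 8% at ρ = 0.3, 0.5 and 0.7. The difference of differences rejects 5%.

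**4. Precision of the position contrast, 15 v 15.** The PSIS-only comparison detects 1.06 SD at 80% power. Relative to it, the variance is 2(1−ρ) for the difference of differences and about 1−ρ² for covariate adjustment. Detectable effects in SD are 1.06 times the square roots:

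| ρ | PSIS only | Difference of differences | Humerus as covariate |
|---|---|---|---|
| 0.3 | 1.06 | 1.25 | 1.01 |
| 0.5 | 1.06 | 1.06 | 0.92 |
| 0.7 | 1.06 | 0.82 | 0.76 |

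The difference of differences gains precision only when ρ exceeds 0.5. Covariate adjustment does not need that, but it removes a shared shift only in part.

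**5. Precision of the site contrast.** At 80% power a paired test detects 0.53 SD of the paired difference with 30 pairs and 0.78 SD with the 15 lateral pairs.

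**The case against.** **Pooling is not stated.** Nowhere does the protocol say that the two PSIS cohorts are merged. Tukey's HSD is needed only with three or more groups, so a three-group ANOVA (prone PSIS, lateral PSIS, humerus) is possible and would separate position from site. This stands as an ambiguity. But section 10 lists two two-way contrasts, Tukey is only an example, and a three-group one-way ANOVA still has no patient term. The pairing and reference points hold on either reading.

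**A position-averaged site effect is a legitimate target.** Section 3.1 names no position, and position varies only for the PSIS harvest. A reader might infer that the primary answer is biased or confounded. The documents do not support that: the d/2 term is bias only if a position-matched answer is meant, and the lateral cohort supplies one. If the true site difference is large, d/2 may not change the conclusion. The background cites a 3.0-fold yield for PSIS against the proximal humerus, though the deep humerus is unquantified.

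**The planned site test is not grossly anti-conservative.** With no lateral site difference, an SD of the log ratio of 0.6 and position ratios of 1.3 and 1.5, a pooled paired test rejects about 20% and 39% of the time. Those rates do not describe the planned test. The unpaired ANOVA gives about 6% and 16% at ρ = 0.5, and 1% and 4% at ρ = 0.7, because ignoring the pairing makes it conservative.

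**Model detail may sit in a SAP.** Covariates and interaction terms often do. Here, however, the protocol itself names a method, and that method conflicts with its own design.

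**Conclusion.** The point holds for section 10; the section 2 sentence on the humeral harvest is not itself wrong. The named one-way ANOVA ignores the pairing, which costs the site test much of its sensitivity when the sites are positively correlated. It also leaves a non-randomised, consecutive-cohort position comparison without the one reference that the trial already collects. On the plainest reading the site estimate also carries half of any position effect. That calls for a stated estimand and is not evidence of a false primary result.

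The sizes depend on the assumed correlations, SDs and shifts. The protection given by the difference of differences further assumes that a shift between cohorts affects both sites equally, which the documents neither support nor exclude. This should be changed before analysis, but it does not undermine the design: the data to be collected are sufficient.

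**What to change.** In section 10, replace the one-way ANOVA with one model containing patient (random effect), site, cohort (prone or lateral PSIS) and site-by-cohort, on the log scale where a measure is skewed.

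- **Site.** State the estimand. Give the equal-weight, position-averaged contrast from all 30 pairs, and also the contrast in each cohort, with the lateral cohort labelled as position-matched.
- **Position.** Report the site-by-cohort interaction (the difference of within-patient PSIS-minus-humerus differences) as the drift-protected estimate, alongside the PSIS comparison adjusted for the humeral value. Say that the first assumes equal shifts at both sites and gains precision only if the between-site correlation exceeds 0.5, and that the second is more precise but removes drift only in part.

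The cost is a change of analysis wording, with no new samples or procedures. The downside is that the position-matched site contrast rests on 15 pairs and is less precise than the 30-pair contrast, so both should be shown.

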3.1 Primary Objective

The primary objective of this study is to determine whether the PSIS or deep humeral harvest produces a greater cellular harvest in patients undergoing rotator cuff repair.

3.2 Secondary Objective

The secondary objective is to determine if prone verses lateral decubitus participant positioning influences the quantity of harvested cells from the PSIS.

3.3 Primary Effectiveness Endpoints

The primary effectiveness endpoints of this study include cellular content measures of cBMA collected from each extraction site (as outlined in section 6.2).

3.4 Secondary Effectiveness Endpoints

The secondary effectiveness endpoints of this study include cellular content measures of cBMA collected from each anatomical position (as outlined in section 6.2).

4 Hypotheses

4.1 Null Hypothesis:

H_0 - Participants will have similar cellular content (*in vitro*) in bone marrow aspirate taken from the PSIS and from deep humeral harvest. Additionally, patient positioning will not affect the cellular content of bone marrow from the PSIS.

4.2 Alternative Hypothesis:

H_1 - Participants will not have similar cellular content (*in vitro*) in bone marrow aspirate taken from the PSIS and from deep humeral harvest. Additionally, patient positioning will affect the cellular content of bone marrow from the PSIS.

5 Participant Recruitment and Screening

5.1 Screening Process:

Once interested participants are identified and prescreened, a screening visit will be scheduled (visit 1). During the screening visit, a screening form will be completed which includes the inclusion and exclusion criterion below. If an individual answers "yes" to any of the initial screening exclusion questions, they will be informed that they do not qualify for the study, and they will be informed that they can keep their screening form and their medical care will not be adversely affected by not enrolling in the study. If all answers are "no" then the form will be placed in the study documents and the enrollment process will continue.

5.1.1 Inclusion Criteria:

- 18-80 years of age
- Diagnosis of a rotator cuff tear requiring arthroscopic rotator cuff repair

5.1.2 Exclusion Criteria:

- Patients who require superior capsular reconstruction or revision rotator cuff repair
- Diabetes
- Immune disorders

- Past medical history of a metastatic or other cancer which required chemotherapy/radiation therapy
- Rheumatoid arthritis
- Is unable to comprehend the study documents or give informed consent

Once the screening requirements are met, the informed consent form will be provided to the participant on paper or electronically via REDCap for review ensure the volunteer understands the details of the study including the benefits and risk factors. The subject will be provided sufficient time to consent and sign the informed consent form (ICF). The principal investigator (PI) and study/research team will be available to answer any questions or provide clarifications during the informed consent process.

5.2 Informed Consent 21 CFR 50

In adherence to the 21 CFR 50, Protection of Human Subjects Guidelines, the informed consent process will be performed by one of the study investigators or staff, in the research office that has received training on the informed consent process. No aspects of the study will be conducted prior to obtaining informed consent from each participant. The purpose and methods of the study along with the expected effects will be reviewed with each potential participant. Each participant will be provided a copy of the consent and sufficient time will be given for the opportunity to read and ask any questions about the study. After signing of the informed consent document, participants will be given a copy for their records.

The designee will review with each participant that they are free to refuse to the study or to withdraw from it at any time.

5.3 Consent Withdrawal:

During the informed consent procedure, participants will be informed that if at any point during the study, consent may be withdrawn. To withdraw consent, participants can request in writing to withdraw HIPAA authorization and the research site will not use or provide any health information to researchers. At this time, the link between the participant's health information will be severed with the research team. This process for consent withdrawal will be reviewed with each participant and identified barriers will be addressed at the time of informed consent.

5.4 Benefits:

Participants may directly benefit from improved healing via cBMA augmentation of their rotator cuff repair as a result of agreeing to participate in the study. Participants will receive at no extra charge cell augmentation therapy of their rotator cuff repair. Indirect benefits include additional medical care and follow-up after surgery. This study may help

direct clinical practice in developing preferred techniques to augment orthopedic surgical procedures (aspirational benefit).

5.5 Compensation:

Compensation will not be provided to participants for participating in this study.

6 Treatment Plan

After the described screening and informed consent process have been completed, all participants will undergo standard-of-care arthroscopic rotator cuff repair surgery. During all surgeries, bone marrow will be aspirated from the PSIS and from the deep humerus. The first 15 participants will have bone marrow aspirated from the PSIS while in the prone position on the operating table and deep humerus during the surgery in the lateral decubitus position. The final 15 participants will have bone marrow aspirated from the PSIS while in the lateral decubitus position on the operating table and deep humerus during the surgery in the lateral decubitus position. Bone Marrow Aspirate will be concentrated at a 12% hematocrit setting independently from each site. One mL of cBMA from each harvest site from each surgery will be removed and sent to the AREF RMC for analysis. The remaining cBMA will be used to augment the rotator cuff repair surgery.

6.1 Surgical Procedure and cBMA Collection:

The first 15 participants will be placed in the prone position on the operative table for the bone marrow harvest from the PSIS. After bone marrow harvest from the PSIS, the patient will be placed in the lateral decubitus position for the rotator cuff repair. Rotator cuff repair is always performed in either the lateral decubitus position or an upright, seated position called the beach chair position. The final 15 participants will be placed in the lateral decubitus position on the operative table for the bone marrow harvest and the rotator cuff repair. The PSIS harvest will be performed first. The skin will be prepped and draped in sterile fashion over the PSIS. Lidocaine 1% will be used to anesthetize the skin around the incision location. A stab incision will be made in the skin over the PSIS. Two 30 cc syringes and a traditional 11-gauge, 11 cm Jamshidi needle (Ranfac Corporation, Avon, MA, USA) will be pre-rinsed with heparin. The two 30 cc syringes will be loaded with 4 cc of anticoagulant citrate dextrose solution-A (ACDA). The needle will be advanced into the bone marrow cavity 3-4 cm. 30 mL of bone marrow will be aspirated while the needle is withdrawn and rotated with one syringe. The needle will then be reinserted divergently, and another 30 mL of bone marrow aspirated with the second syringe. This method has been described and quantitatively studied with similar harvest to a multiple puncture technique (18). A sterile dressing will be applied. The participant will be re-prepped and draped in standard fashion for shoulder arthroscopy. A diagnostic arthroscopy will be performed, and the rotator cuff tear identified. While

viewing from the standard posterior portal in the subacromial space, a spinal needle will be used to localize the location and trajectory for placement of the first suture anchor for the rotator cuff repair. Once the placement of the proposed anterior suture anchor is confirmed, the 11-gauge bone marrow harvest needle will be placed into this location and the arm adducted. The needle will then be advanced into the humeral diaphysis as far as the needle length allows. Two 30 mL syringes will be pre-filled with 4 mL of ACD-A and used to harvest 60 mL of bone marrow aspirate. The bone marrow samples will then be processed independently using the Arthrex Angel blood processing system (Arthrex, Naples, FL) using the 12% hematocrit setting with two separate disposables. One mL of cBMA from each harvest site will be removed and sent to the AREF RMC for analysis. The remaining cBMA will be used to augment the rotator cuff repair surgery.

6.2 Cellular Analysis:

Cellular analysis of each cBMA sample from the two collection sites per participant will include a Complete Blood Cell (CBC) count, a Total Nucleated Cell (TNC), viability count, and cell culture analysis.

The CBC count will be performed using an automated hemocytometer (XN-350; Sysmex, Kungsbacka, Sweden) and will include red blood cell (RBC), white blood cell (WBC), monocyte, platelet, and hematopoietic progenitor cell (HPC) concentration.

The TNC and viability count will be performed using an automated cell counter.

Cell culture experiments will include Colony Forming Unit-fibroblast (CFU-F) counts and the potential for additional stem or progenitor cell analysis procedures. If stem or progenitor cells are observed during culturing, additional experiments will be conducted to analyze differentiation potential (differentiation assays) and cell-surface markers (flow cytometry).

7 Review of Safety

7.1 Adverse Event (AE)

An adverse event is any untoward or unfavorable medical occurrence in the human subject, including any abnormal sign, symptom, or disease, temporally associated with the subject's participation in the research, whether considered related to the subject's participation in the research.

